36.	Partial Waiver of Consent for Screening/Recruitment	25
37.	Partial Waiver of HIPAA Authorization for Screening/Recruitment.....	26
38.	Waiver of Documentation of Consent	26
39.	Alteration of Consent.....	27
40.	Full Waiver of Consent/Parental Permission.....	28
41.	Full Waiver of Consent/Parental Permission (Public Benefit or Service Programs)	
	29	
42.	Full Waiver of HIPAA Authorization (Checklist).....	29
43.	Other Waiver Types (Checklist).....	30

44.	Vulnerable Populations (Checklist).....	30
45.	Medical Devices (Checklist).....	36
46.	Export Control (Checklist)	37
47.	Data Transfer/Sharing (Checklist).....	37
48.	Specimen Transfer/Sharing (Checklist).....	38

1. Objectives

1.1. Describe the purpose, specific aims, or objectives.

Our long-term goal is to develop a mindfulness-based intervention (MBI) program that significantly decreases stress/burnout and increases belongingness and connectedness among nurse faculty and staff. The overall objective of this pilot project, which is the next step in toward achievement of our long-term goal, is to examine the feasibility and preliminary efficacy of MBIs as an intervention for University of New Mexico (UNM) Health Sciences Center (HSC) nurse faculty and staff. Our central hypothesis is that this MBI intervention will improve the psychosocial outcomes (sense of belonging) and physiological outcomes (HRV) among HSC nurse faculty and staff. To test our central hypothesis and attain the overall objective, we will pursue the following specific aims:

Aim 1. To evaluate the feasibility and acceptability of MBIs (meditation or yoga) for HSC nurse faculty and staff. Acceptability will be assessed qualitatively from analyses of interviews with participants. Feasibility will be assessed as rates of recruitment, retention, and adherence to the MBI (% training sessions attended).

Aim 2. To evaluate the preliminary effect of MBI (meditation; yoga) in HSC nurse faculty and staff on: psycho-social outcomes (burnout; sense of belonging, stress, anxiety) and physiological outcomes (HRV evaluated by wearable electronics). We hypothesize that: a) psycho-social outcomes will improve post-intervention and b) physiologic measures (HRV) will improve post intervention compared to preintervention.

1.2. State the hypotheses to be tested.

Our central hypothesis is that this MBI intervention will improve the psychosocial outcomes (sense of belonging) and physiological outcomes (HRV) among HSC nurse faculty and staff.

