The UNM CON currently employs 71 faculty and 71 staff and the HSC has additional nurse faculty and staff. We will employ a quasi-experimental design to assess feasibility, acceptability, and preliminary efficacy of MBIs (meditation; yoga) to increase a sense of belonging and connectedness in academic nursing faculty and staff. Using convenience sampling we will recruit and enroll 60 participants in to two study groups: 1) mindfulness mediation and 2) yoga. Interested study participants will be contacted by study staff and screened to determine study eligibility (See Attachment A). The screener is approximately 1-page in length and takes approximately 5 minutes to complete. The screener includes queries related to inclusion and exclusion criteria. Participants will also complete an Exercise Participation Screening (see Attachment B).¹⁷

Pre-data collection:

We will assign 15 individuals to each condition. Across both conditions, all participants will participate in one baseline assessment/training session, 6 weeks of MBIs (participants will be required to attend 2 sessions per week), and a post-intervention assessment session. Following screening for inclusion/exclusion criteria, eligible participants will complete the BEING Mindful Exercise participation screening. Eligible participants will provide informed consent.

After informed consent is obtained, research staff will allocate individuals to meditation vs yoga on 1:1 basis. If an individual is unable to participate in the yoga arm based on the BEING Mindful Exercise participation screening, they will be assigned to meditation and the next two participants will be assigned to yoga.

All participants will be given an anonymous study ID number once they are enrolled in the study. The only link between the study ID number and any identifier will be stored in a secure N:\Research-Studies network drive, in a folder to which only the investigators will have access. Any link between the study ID and identifiers will be destroyed when data analysis is complete.

Once we have enrolled 30 participants we will waitlist individuals for a second six-week intervention session after the completion of the first session. This will result in a possible enrollment 60 individuals.

12.3. For studies that collect existing or prospective data, describe the source of information, whether collected prospective or retrospectively.

Data collection:

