Description of Intervention Delivery

These guidelines detail the procedures used to conduct Mindful Meditation or Yoga sessions.

We will employ a quasi-experimental design to assess feasibility, acceptability, and preliminary efficacy of MBIs (meditation; yoga) to increase a sense of belonging and connectedness in academic nursing faculty and staff. We will assign 15 individuals to each condition. Across both conditions, all participants will participate in one baseline assessment/training session, 6 weeks of MBIs (participants will be required to attend 2 sessions per week), and a post-intervention assessment session. Following screening for inclusion/exclusion criteria, eligible participants will complete the **BEING Mindful** Exercise participation screening. Eligible participants will provide informed consent.

Assignment of Participants:

After informed consent is obtained, research staff will allocate individuals to meditation vs yoga on a 1:1 basis. If an individual is unable to participate in the yoga arm, they will be assigned to meditation and the next two participants will be assigned to yoga.

Retention:

To promote retention, we will reach out to participants with frequent reminders via text messages and emails.

Baseline Assessment session: During the baseline assessment session, participant characteristics will be collected. Baseline self-report questionnaires will be completed: 1) Sense of Belonging Scale (SBS); 2) Mindfulness Attention Awareness Scale (MASS) 15-item; 3) Generalized Anxiety Disorder-7 (GAD-7); 4) NIH toolbox measure of perceived stress.

Intervention Delivery:

The meditation and yoga interventions are 6-week protocols. We will offer meditation sessions 4 times per week and yoga sessions 4 times per week. We will require participants to attend two sessions per week. Attendance will be tracked via the Ilumivu platform. Participants will be requested to log attendance at each session via the app.

The meditation intervention will be led by [name] and [name]. Meditation is a practice of mental exercises designed to increase focus and cultivate a desire to relieve suffering in self and other.^{35,36} The practice dates back millennia to Buddhist and Hindu sages, but more recent work focuses on stress.³⁷ More recently, the term mindfulness has been used which means awareness, attention, and remembering.³⁷ Many religious traditions have a form of meditation based practice. This study will focus

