Aim 1: To assess precision of estimates, 95% confidence intervals will be calculated for rates of recruitment into study, retention to end of study, and participants completing all training sessions. Overall adherence will also be described by calculating the mean and standard deviation of the number of completed training sessions per participant. Qualitative Analyses: Qualitative descriptive analysis⁴⁰ will be used to create a comprehensive summary of the acceptability of the MBI to participants. Deductive analysis will be used to determine common themes related to acceptability in the domains of affective attitude, burden, ethicality, intervention coherence, opportunity costs, perceived effectiveness, and self-efficacy.⁴¹ Interview responses will be reviewed by two members of the research team to identify themes. Themes and preliminary interpretations will be regularly presented to the larger research team to resolve any discrepancies or disagreements and check for alternative interpretations.

Aim 2: Participant characteristics and baseline survey responses will be described using means and standard deviations (SD) for continuous variables and number (percentage) for categorical variables. Continuous intervention outcomes will be described using means and standard deviations and, due to sample size, difference scores from baseline for intervention outcomes will be compared between groups using non-parametric statistical tests. Cohen's d, as a descriptive statistic, will be used as an effect size measure to quantify the extent of within group and between group differences in means over time.⁴² Long-term HRV (time domain and frequency domain measures derived for each 5 minute epoch within a 24 hour period will be averaged) measures will be compared between meditation and yoga groups by t-test. EMA and HRV data will be merged into a single dataset, matching upon timestamp.

Five-minute heart rate epochs immediately following completion of each mEMA survey will be selected for analysis.^{20,34}

13.2. Provide a power analysis, if applicable.

14. Provisions to Monitor the Data to Ensure the Safety of Subjects

This section is required when research involves more than Minimal Risk to subjects. Describe:

N/A – The PI believes this study constitutes no more than minimal risk for potential participants. Therefore, a Data and Safety Monitoring Plan is not required.

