There are minimal risks to participants from this research. Since breach of confidentiality is the most likely risk, participants will be administered informed consent privately in order to insure anonymity. All data collected as part of the study will be identified with a study number. Any forms and survey results that are obtained will be securely stored in either an encrypted database or on the N:\Research-Studies network Drive. Any links between personal identifying information and study ID will be destroyed upon completion of the study.

Each participant will complete surveys regarding mental well-being (e.g. anxiety, stress). These surveys may cause discomfort or stress. To minimize stress, all interviews will be conducted in a private room in a non-judgmental manner by trained research personnel. We will encourage all study participants to discuss concerns about mental health or other health issues with their health-care provider. Additionally, meditation is generally not considered harmful, however, it is possible a participant may experience some discomfort while participating in meditation. Meditation can reveal uncomfortable thoughts or emotions. If a participant experiences distress, a trained research team member will provide the participant with information related to the UNM Counseling, Assistance, & Referral Services (CARS).

Yoga is generally considered to be a safe form of physical activity when performed properly under the guidance of trained instructors. However, as with other forms of physical activity, there is always a chance that an injury may occur. Most common discomforts include muscle soreness, pain, fatigue, or emotional discomfort. We will ask participants to complete an Exercise Participation Screener to determine exercise readiness. The certified yoga instructors are trained to provide guidance on modifications to make sure everyone can participate safely. In the rare event of an injury, research personnel will assist the participant to make an appointment at the UNM LoboCare Clinic.

18.3. If applicable, indicate which procedures may have risks to an embryo or fetus should the subject be or become pregnant. If pregnancy testing or birth control provisions are required, describe these.

N/A

18.4. If applicable, describe risks to others who are not subjects.

N/A

18.5. Describe the steps being taken to minimize the probability or magnitude of risks.

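### Section 13.1 compares yoga with meditation but does not say how participants barred from yoga by the exercise screen are handled, so any such participants can confound the comparison

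*Combined protocol and SAP*

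**What the plan says.** Section 12.2 (pre-data collection) sets the order of events. After the inclusion and exclusion check, "eligible participants will complete the BEING Mindful Exercise participation screening"; consent follows, and then staff allocate 1:1 to meditation or yoga, 15 to each condition. For someone ruled out of yoga by that screen, "they will be assigned to meditation and the next two participants will be assigned to yoga". Section 12.5 (Assignment of Participants) repeats the rule without naming the screen: "If an individual is unable to participate in the yoga arm, they will be assigned to meditation".

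Section 13.1, Aim 2, then compares the arms in three ways:

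- For the intervention outcomes, "difference scores from baseline for intervention outcomes will be compared between groups using non-parametric statistical tests".
- Cohen's d, labelled descriptive, is to "quantify the extent of within group and between group differences in means over time".
- Long-term HRV "measures will be compared between meditation and yoga groups by t-test", with no baseline term stated.

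Nothing in 13.1 defines an analysis set for these comparisons, or a restriction, adjustment or sensitivity analysis for participants who could not have been given yoga. Physical ability is recorded at baseline (Section 12.3), but 13.1 uses participant characteristics only for description.

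**The concern.** The rule works in one direction. A participant who passes the screen can be placed in either arm; one who fails can be placed only in meditation. The meditation arm is then a mixture of people eligible for both interventions and people restricted on health grounds, while the yoga arm contains only the former. This imbalance is written into the allocation rule and is not a chance result.

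The outcomes are not equally exposed. Difference scores remove stable differences in level, so the questionnaire comparisons are biased only if restricted participants change by a different amount. The long-term HRV t-test states no baseline term, so a difference in level is enough. Section 2.3 itself presents HRV as a marker of health, which makes such a difference plausible.

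At stake is the reading of the only significance tests that 13.1 names: a health-status difference could be taken for a difference between yoga and meditation. Section 13.1 also wants estimates for powering a later R01 application, without saying which. If the between-group d is used, it carries the bias. Aim 1 and the within-group pre-post summaries are not affected by this bias.

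**Working it through.** **Inputs from the documents.** 15 per arm in a cohort of 30 (Sections 12.2 and 5.2), so 30 per arm if both cohorts fill and are pooled. The plan gives no screen-failure rate, no outcome SD and no between-arm figure on this point, so there is no stated result to reproduce. The exercise screen itself (Attachment B) is not among the public documents.

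**Assumptions.** k is the number of restricted participants in the meditation arm. The gap is the difference in mean outcome (change for the questionnaires, level for HRV) between restricted and unrestricted participants, in SD units. Arms are taken as 15 v 15 or 30 v 30, with a normal outcome, no true arm effect and a 5% two-sided test. Mann-Whitney stands in for the unnamed non-parametric test.

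**Step 1: bias.** Bias in the arm difference = (k / n in meditation) × gap.

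- 1/15 × 0.5 = 0.033 SD
- 2/15 × 1.0 = 0.133 SD
- 3/15 × 1.0 = 0.200 SD
- 5/15 × 1.0 = 0.333 SD

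The same proportions with 30 per arm give the same bias.

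**Step 2: comparison with sampling error.** Standard error of the arm difference = √(2/n), which is √(2/15) = 0.365 SD for one cohort and √(2/30) = 0.258 SD pooled. Within one cohort every bias above is below one standard error. Pooled, the extreme (0.333) exceeds it.

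**Step 3: error rate by simulation** (60,000 runs for the t-test, 20,000 for Mann-Whitney).

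| Per arm | k | Gap (SD) | Bias (SD) | t-test | Mann-Whitney |
|---|---|---|---|---|---|
| 15 | 1 | 1.0 | 0.067 | 5.0% | 4.5% |
| 15 | 2 | 1.0 | 0.133 | 5.7% | 5.2% |
| 15 | 3 | 1.0 | 0.200 | 7.1% | 6.2% |
| 15 | 5 | 0.5 | 0.167 | 6.9% | 6.2% |
| 15 | 5 | 1.0 | 0.333 | 12.1% | 10.2% |
| 30 | 2 | 1.0 | 0.067 | 5.0% | 4.7% |
| 30 | 4 | 1.0 | 0.133 | 7.1% | 6.6% |
| 30 | 6 | 1.0 | 0.200 | 10.2% | 9.2% |
| 30 | 10 | 1.0 | 0.333 | 21.1% | 19.5% |

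For a fixed proportion restricted, pooling the cohorts leaves the bias unchanged while the standard error shrinks, so the error rate rises.

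**Step 4: the same scenarios among screen-passers only.** If passers are alike in both arms, the t-test rejects in 4.8% to 5.1% of runs and Mann-Whitney in 4.2% to 5.0%, with mean bias within 0.002 SD of zero.

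**Step 5: precision lost.** Standard error = √(1/n + 1/(n − k)).

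- One cohort, against 0.365: k = 1 gives 0.372 (+1.8%); k = 2 gives 0.379 (+3.8%); k = 5 gives 0.408 (+11.8%).
- Pooled, against 0.258: k = 2 gives 0.263 (+1.8%); k = 10 gives 0.289 (+11.8%); k = 12 gives 0.298 (+15.5%).

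**The case against.** The strongest reply is that the problem may hardly arise. Section 4.2 requires general good health, excludes major illness that prevents participation, and describes the exercise guidelines as meant to lower barriers. Section 4.4 excludes pregnancy. The yoga manual offers modified poses (Section 12.5), and Section 18 describes the instructors as "trained to provide guidance on modifications to make sure everyone can participate safely". At one or two failures per cohort the error rate stays close to nominal. This stands, and it limits the weight of the point.

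The comparison is also not the main purpose. Feasibility and acceptability are the primary outcomes (Section 7.1), the design is declared quasi-experimental (Section 3.1), d is descriptive, and the Aim 2 hypotheses are pre-post: HRV, for instance, "will improve post intervention compared to preintervention". This stands too, but it bears on severity only: 13.1 still tests the arms against each other, and a non-randomised design gives more reason to deal with a selection route that is known and measured.

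A single assumed gap serves for both change scores and HRV level. Nothing in the documents supports a full 1.0 SD difference in change, so the Mann-Whitney extremes are the less credible ones and HRV is the real exposure. That is fair.

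Restricting to screen-passers does not make the arms comparable in other respects: staff allocate, and no random or concealed sequence is described. That is true. The restriction removes this one route only.

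Finally, reporting the count and adding a screen-passer sensitivity analysis might be enough. With very few failures the two approaches would give nearly the same answer. But only screen-passers could have entered either arm, so they are the natural population for the main contrast, and choosing them costs almost nothing when failures are few. Recording physical ability does not replace this, since 13.1 does not use it in the tests.

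**Conclusion.** The concern holds. Followed as written, the plan confounds the arm comparison whenever anyone fails the exercise screen and differs from the rest in the relevant way. The size cannot be known from the documents. On the assumed k and gap it runs from zero with no failures, through 0.03 to 0.13 SD and an error rate of about 5% to 6% at 1 or 2 restricted of 15, to 0.33 SD at 5 of 15. At that extreme the error rate is about 12% (t-test) or 10% (Mann-Whitney) in one cohort, and about 21% or 20% if both cohorts are pooled at 10 of 30. The lower end is the more plausible given the eligibility criteria. The change should be made because it is cheap and the problem is foreseeable. It does not threaten the pilot's primary outcomes. Confidence is medium, because everything about size rests on assumptions.

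**What to change.** In 13.1, state that the between-arm tests and the between-group Cohen's d are made among participants who passed the exercise screen, and that the same comparison in all participants is a sensitivity analysis. Settle this before outcomes are seen. Record the screen result as a flag at the point where 12.2 places it, before consent and allocation, and bring 12.5 into line by naming the screen. Keep restricted participants in Aim 1 and in the within-group summaries, and report how many there were.

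The cost is a few sentences and one recorded flag, with no change to enrolment or allocation. In one cohort the main comparison becomes 15 yoga v 14, 13 or 10 meditation with 1, 2 or 5 restricted, and the standard error rises by about 2%, 4% or 12%. Pooled at about 30 v 30, with 2, 10 or 12 restricted, it becomes 30 v 28, 20 or 18, a rise of about 2%, 12% or 15%. If nobody fails there is no cost.

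This does not cure other baseline HRV imbalance between non-randomised arms, which is a separate matter. Recording restricted participants outside the 1:1 sequence and allocating the others from a concealed random list would be an optional design change; this fix does not depend on it.

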It is long been established that mindfulness practices like meditation and yoga are associated with positive mental health outcomes.^{8,9} In addition, mindfulness practices are known to support interpersonal relationships.¹⁰ In the workplace, mindfulness practice improves communication, builds a sense of shared goals leading to greater productivity and retention, and helps to decrease burnout.^{11,12} Furthermore, mindfulness practices foster resilience. Mindfulness practices are also associated with improved physiologic function including autonomic nervous system (ANS) function.¹³ Peripheral ANS activity, including cardiac vagal activity (indexed by heart rate variability [HRV]), regulates dynamic fine-tuning of feedback loops between emotion-related brain circuitry and the heart.¹⁴ HRV is known to be a robust biomarker of health, wellness, stress, and the ability to self-regulate.¹⁵ By instructing individuals in MBIs homeostasis in brain-heart feedback loops is promoted leading to autonomic stability.¹⁶ Given the potential impact of MBI to promote individual and workplace wellness, investigation of this intervention to improve wellness in academic faculty and staff is critical.

3. Study Design

3.1. Describe the study design (e.g., observational; randomized placebo-controlled clinical trial, etc.)

This study is a minimal-risk, single site, quasi-experimental study.

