5.3. Provide sample size justification

The planned overall sample size of 30 is consistent with recommendations for pilot studies seeking to build evidence in the context of medium effect size differences between two groups.¹⁸

6. Study Timelines

6.1. Describe:

- *The duration of an individual subject's participation in the research*
- *The duration anticipated to enroll all subjects*
- *The expected duration for the investigators to complete the study (complete analysis)*

Participants will be enrolled until the allotted 30 participants for the first 6 weeks of the study is reached. The study is comprised of a pre-intervention assessment, followed by 6 weeks of meditation/yoga attendance (twice/week). Upon completion of the 6-week intervention, participants will complete a post intervention assessment (See Table 1.).

Table 1. Study Timeline	Months									
	1	2	3	4	5	6	7	8	9	10
Prepare research and data management tools.		→								
Session 1										
Recruitment		→								
Intervention		→	→							
Data Collection		→	→							
Preliminary Data Analyses				→						
Session 2										
Intervention				→						
Data Collection				→						
Analyses					→					
Prepare R01 proposal										→
Dissemination										→

7. Study Endpoints: Primary endpoint(s) are typically efficacy measures that address the main research question. Secondary endpoints are generally not sufficient to influence decision-making alone, but may support the claim of efficacy by demonstrating additional effects or by supporting a causal mechanism.

7.1. *Describe the primary and secondary study endpoints.*

Primary outcomes of interest of this study include the feasibility and acceptability of mindfulness-based interventions (MBI) (Aim 1). We will also examine the preliminary effect of these interventions on psychosocial outcomes (primary: sense of belonging; secondary: burnout, stress) and physiologic outcomes (HRV) (Aim 2).

7.2. *Describe any primary or secondary safety endpoints.*

This is a minimal risk study.

7.3. *Describe any exploratory endpoints.*

N/A There are no anticipated exploratory endpoints.

8. Research Setting

8.1. *Describe the sites or locations where your research team will conduct the research.*

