Feasibility of recruitment: The UNM CON currently employs 71 faculty members and 71 staff members with additional nurse faculty in other HSC schools and colleges and the hospital. The planned overall sample size of 30 per cohort is consistent with recommendations for pilot studies seeking to build evidence in the context of medium effect size differences between two groups.¹⁸ Furthermore, objectives of pilot studies include assessment of recruitment and retention rates.¹⁸

The UNM College of Nursing is housed in the College of Nursing/College of Population Health Building. The UNM College of Nursing has a state-of-the-art Research Laboratory suite that includes private clinical research rooms as well as a large collaborative research space to conduct the intervention.

This is a minimal risk study that is not expected to have adverse psychological or medical consequences for participants. However, if needed there are providers available for referral and referral procedures are described below in Section 18 - Risks to Subjects.

Prior to beginning recruitment and enrollment, all study personnel will be trained on the protocol as well as consent and interview procedures for the study. All study personnel will have completed training for the ethical conduct of research. Study coordinators will routinely monitor the approved study team member list to ensure all team members remain current in their training.

10. Prior Approvals

- 10.1. *Describe any approvals that will be obtained prior to commencing the research. (e.g., school, external site, funding agency, laboratory, radiation safety, or biosafety approval.)* N/A
- 10.2. *Upload the required Departmental Review Form signed by your Department Chair (or authorized designee if the PI is the Department Chair) into Huron IRB under “supporting documents.” The signed, required Departmental Review form has been uploaded under “supporting documents”.*

10.3. If a study includes ionizing radiation, the Radiation Safety Attachment (HUS-FORM_1) must be uploaded (attached) in Huron IRB with your submission. The consent should include radiation exposure information in the Risks section.

N/A

10.4. If applicable to the study, include the signed “Biological Specimens” and/or “Drug Attachment” in Huron IRB with your submission.

N/A

11. Multi-Site Research

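### The make-up rule for people who cannot do yoga ignores which arm was due, so it can over-fill yoga, and it cannot be followed when one of the next two is also unable

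*Combined protocol and SAP*

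**What the plan says.** Section 12.2 (Pre-data collection) sets the allocation: "After informed consent is obtained, research staff will allocate individuals to meditation vs yoga on 1:1 basis". The target is stated just before: "We will assign 15 individuals to each condition". Fifteen per condition fits one cohort, since Section 9 says "The planned overall sample size of 30 per cohort is consistent with recommendations for pilot studies" and up to two cohorts are planned.

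Ability to do yoga is known before the arm is assigned: "Following screening for inclusion/exclusion criteria, eligible participants will complete the BEING Mindful Exercise participation screening", with consent and allocation afterwards.

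The exception begins "If an individual is unable to participate in the yoga arm based on the BEING Mindful Exercise participation screening" and continues "they will be assigned to meditation and the next two participants will be assigned to yoga". Section 12.5 (Assignment of Participants) repeats it without naming the screen.

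Neither section makes the exception depend on the arm that was due. Neither says what to do if one of the following two people is also unable, how the base order is generated, or whether 15 is a ceiling that overrides the make-up. On design, Section 3.1 says only "This study is a minimal-risk, single site, quasi-experimental study".

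**The concern.** Two yoga assignments in a row repair the balance when an unable person has taken a place meant for yoga. When that person was due for meditation anyway, no repair is needed, yet the two yoga assignments still follow. The error is either zero or in favour of yoga, so it does not average out.

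The rule also has no exit. If the next person, or the one after, fails the exercise screen too, one clause sends that person to yoga and the other to meditation. Research staff would have to improvise at the moment of allocation, knowing who the participant is.

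Section 13.1 compares difference scores and long-term HRV between the meditation and yoga groups, so the way people reach each arm bears on a planned analysis. After each unable person, staff also know the next two assignments, which leaves room to time enrolment around a preferred class.

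**Working it through.** **Inputs.** From the documents: 30 per cohort (Section 9); 1:1, 15 per condition, and the exception (Sections 12.2 and 12.5). Assumed, because the documents give no figure: 5%, 10% or 20% of participants unable to do yoga; d = 0.5 for the "medium effect size differences between two groups" of Section 5.3.

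**The plan's figure.** 30 × 1/2 = 15 per condition. It reproduces.

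**One unable person on a fixed alternating list** (M meditation, Y yoga, unable person in brackets):

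- Yoga was due: M Y M [M] Y Y M Y. After eight people 4 M and 4 Y; the cohort ends 15/15.
- Meditation was due: M Y [M] Y Y Y M Y. After eight people 3 M and 5 Y; the cohort ends 14 M / 16 Y.

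This held for the unable person at each of positions 1 to 28, for either starting arm, and whether the two forced places use up list slots or pause the list.

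**Whole cohorts.** 20,000 simulated cohorts of 30 per setting, no cap at 15. An unable person arriving while yoga places are owed goes to meditation and the count of two starts again. Excess = 2 × (mean yoga) − 30.

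| Share unable | Mean yoga (fixed alternating list) | Mean excess | Yoga at least 2 ahead |
|---|---|---|---|
| 5% | 15.57 | 1.14 | 46% |
| 10% | 15.93 | 1.86 | 65% |
| 20% | 16.11 | 2.22 | 70% |

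The base method matters, and the plan does not state it:

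- If alternation restarts from the last arm given, yoga is at least 2 ahead in 28% to 44% of cohorts, and the mean excess is about 0.5 at 5% unable.
- With a coin toss the figure is 52% to 62%, but a fair coin alone gives P(Y ≥ 16 of 30) = 43%. The rule therefore adds about 9 to 19 percentage points. The mean excess is 1.1 to 2.2.

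**The clash.** Per unable person, the chance that at least one of the next two is also unable is 1 − (1 − p)²: 9.75%, 19% and 36%. A cohort has no clash only if all unable people are at least three places apart:

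P(no clash) = Σₖ C(30 − 2(k − 1), k) pᵏ (1 − p)³⁰⁻ᵏ

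At p = 0.05 the terms for k = 0 to 5 are 0.215 + 0.339 + 0.225 + 0.081 + 0.018 + 0.002 = 0.880, so a clash occurs in 12% of cohorts. At p = 0.10 the sum is 0.624 (38%); at p = 0.20 it is 0.188 (81%). Simulation agrees.

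**Power.** Φ(d / √(1/n_M + 1/n_Y) − 1.96) with d = 0.5:

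- 15/15: Φ(0.5/0.365 − 1.96) = 27.7%
- 14/16: 27.6%
- 13/17: 27.3%

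**Foreknowledge.** About 3 to 8 of 30 assignments are forced yoga places at 5% to 20% unable. Under simple alternation all 30 are predictable already.

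**A make-up triggered only by a displaced yoga place.** Under alternation, one unable person then gives 15/15 at every position tested, and yoga never reaches 16 at any share from 3% to 20%.

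**The case against.** The case against is substantial, and much of it stands.

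- The target of 15 per condition could be read as a cap, and then yoga never finishes above 15. But the text does not say which instruction prevails, and a cap does not resolve the clash.
- A reader might infer that the rule always over-fills yoga. It does not: when yoga was due it is exactly right.
- A reader might infer that the rule breaks the concealment of a randomised comparison. The documents claim neither randomisation nor concealment. If the base method is simple alternation, the rule adds no predictability; the unstated base method is then the larger gap.
- A reader might say that able participants are denied 1:1 by this rule. Any scheme that holds 15/15 while placing k unable people in meditation splits the able 15 yoga to 15 − k meditation, so this is not peculiar to the make-up sentence.
- Materiality is small. Section 7.1 makes feasibility and acceptability primary, the Aim 2 hypothesis in Section 1.1 is pre-post, and power barely moves. The 81% figure needs 20% unable, which may be high given general good health as an entry criterion (Section 4.2) and yoga modifications and props (Section 12.5).

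What remains is that the sentence, as worded in two places, over-corrects when meditation was due and gives incompatible instructions when unable people arrive close together.

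**Conclusion.** The point holds as a fault in a stated rule, not as a threat to power. By its own words the rule turns 15/15 into 14/16 on a fixed alternating list whenever a single unable person was due for meditation, unless an unstated cap intervenes. Across base methods and 5% to 20% unable, the mean excess of yoga over meditation is about 0.5 to 2.2 people per cohort. The rule cannot be followed literally in about 12%, 38% or 81% of cohorts at 5%, 10% or 20% unable.

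The over-fill in a meditation slot and the contradiction follow from the text alone. The frequencies rest on the assumed share unable, and the imbalance figures also on the base method and on there being no cap. Foreknowledge of the next two assignments is an added harm only if the base method is not simple alternation. The sentence should be corrected before a cohort is allocated.

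**What to change.** Replace the make-up sentence in both 12.2 and 12.5 so that it says:

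- A participant unable to do yoga is placed in meditation, as now. A yoga make-up is owed only if the place due was yoga, one make-up per displaced yoga place.
- The make-up converts the next meditation place due to someone able to do yoga. It is carried forward past anyone else who is unable.
- Fifteen per condition is the limit for participants who can do either arm. An unable person who arrives after meditation is full is still placed in meditation, and the resulting count is reported.

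Preferably, draw the base order for each cohort from a random list of 15 meditation and 15 yoga places, held in REDCap (already in use) and opened one place at a time after consent. This is separable: the wording change works with any base order.

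The cost is one replaced sentence in two places and, if adopted, a list set up in REDCap. No participants or visits are added. There are two downsides. Owed yoga places stay predictable until filled, sometimes for more than one participant. Exact 15/15 can still be missed when an unable person arrives late: in about 5%, 10% and 23% of cohorts at 5%, 10% and 20% unable under a random 15/15 list.
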